8. SECONDARY STATISTICAL ANALYSES

8.1. Efficacy Analyses

8.1.1. Overview of Planned Efficacy Analyses

The secondary efficacy analyses will be based on the “Analysis” population, unless otherwise specified.

Table 3 provides an overview of the planned efficacy analyses with further details of data displays being presented in Appendix 11.10: List of Data Displays.

Table 3 Overview of Planned Efficacy Analyses

Endpoints	Absolute				Change from Baseline			
	Summary		Individual		Summary		Individual	
	T	F	F	L	T	F	F	L
Graft function								
Serum creatinine	Y	Y	Y	Y	Y	Y	Y	Y
Creatinine - AUC	Y			Y				
Creatinine – ½ life	Y			Y				
Urine output			Y	Y				Y
Primary Non Functions	Y			Y				
Functional DGF	Y			Y				
Intermediate graft function	Y			Y				
Immediate graft function	Y			Y				
Acute rejection risk and rejection/PD biomarker								
Episode of biopsy-proven acute rejection	Y			Y				
Serum IP-10	Y	Y	Y		Y	Y	Y	
Serum Mig	Y	Y	Y		Y	Y	Y	
Serum IL-18 levels								
Free IL-18	Y	Y	Y		Y	Y	Y	
Bound IL-18	Y	Y	Y		Y	Y	Y	
Total IL-18	Y	Y	Y		Y	Y	Y	
Urine biomarkers								
IL-18	Y	Y		Y				
NGAL	Y	Y		Y				
KIM1	Y	Y		Y				
Dialysis dependency and graft survival								
Number of dialysis events per patient in the first 30 days post transplant	Y			Y				
Proportion of subjects who are dialysis-independent at visits up to 12 months post transplant	Y							

Exploratory								
% free GSK1070806 within renal graft biopsies	Y			Y				
% bound GSK1070806 within renal graft biopsies	Y			Y				
Level of IL-18 in renal preservation fluid	Y			Y				
Serum IL-18 binding protein			Y					
Serum cytokine levels	Y		Y			Y	Y	
Histological analysis of biopsies with respect to cellular infiltrate								Y
Length of hospital stay	Y			Y				
Re-hospitalization				Y				

NOTES :

- T = Table, F = Figure, L = Listing, Y = Yes display generated.
- Stats Analysis = Represents TFL related to any formal statistical analyses (i.e. modelling) conducted.
- Summary = Represents TFL related to any summaries (i.e. descriptive statistics) of the observed raw data.
- Individual = Represents FL related to any displays of individual subject observed raw data.

8.1.2. AUC and $\frac{1}{2}$ Life Time

For serum creatinine, the 7-Day Area under the Curve (AUC), 30-Day AUC and 30 Day $\frac{1}{2}$ life time will be calculated. The formula to calculate the AUC is:

$AUC = \sum_{i=1}^M 1/2(Y_i + Y_{i-1})(d_i - d_{i-1})$ where Y_i is the serum creatinine value at Day d_i and M is the total number of measures the patient has. The 7 Day AUC will be calculated based on patients who have serum creatinine value at Day 7. The patients who will be discharged before Day 7 will be excluded from calculation. All patients are expected to have serum creatinine 30 Day post transplant. If the value is missing, the patient will be excluded from calculation.

The algorithm to determine the $\frac{1}{2}$ life time is:

1. Determine the $\frac{1}{2}$ value by $Y_{1/2} = \frac{1}{2} * Y_0$ where Y_0 is the baseline value for non-DGF patient and the value after dialysis finished for DGF patient. Denote the corresponding day d_0

2. Find the time interval between d_0 and 30 where $Y_{1/2} < Y_i$ and $Y_{1/2} > Y_{i+1}$. If no such interval, then report “NA” for that patient.

3. The approximate $\frac{1}{2}$ life time is $d_{1/2} = \frac{Y_{1/2} - Y_i}{Y_{i+1} - Y_i} (d_{i+1} - d_i) + d_i$

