11.9.4. Efficacy Tables

Efficacy Tables					
No.	Population	IDS / TST ID / Example Shell	Title	Programming Notes	Deliverable
DGF					
2.01	Analysis Population	Non-Standard EFF_T3	Proportion of Subjects with DGF		IA1, IA2, SAC
2.02	Per Protocol	Non-Standard EFF_T3	Proportion of Subjects with DGF		IA2, SAC
Graft function					
2.03	Analysis Population	Non-Standard EFF_T1	Summary Statistics of Serum Creatinine		IA1, IA2, SAC
2.04	Analysis Population	Non-Standard EFF_T2	Summary of Serum Creatinine Change from Baseline		IA1, IA2, SAC
2.05	Analysis Population	Non-Standard EFF_T1	Summary Statistics of AUC of 7 Day Serum Creatinine	Only consider patients who have Day 7 serum creatinine value	IA1, IA2, SAC
2.06	Analysis Population	Non-Standard EFF_T1	Summary Statistics of AUC of 30 Day Serum Creatinine		IA1, IA2, SAC
2.07	Analysis Population	Non-Standard EFF_T1	Summary Statistics of $\frac{1}{2}$ -Life of 30 Day Serum Creatinine		IA1, IA2, SAC

Efficacy Tables					
No.	Population	IDSL / TST ID / Example Shell	Title	Programming Notes	Deliverable
2.08	All Subjects	Non-Standard EFF_T4	Proportion of Subjects with Renal Functional Graft within 7 Days after Transplant	Including primary non function;3 day functional DGF; 7 day functional DGF; 3 day intermediate graft function; 7 day intermediate graft function; 3 day immediate graft function; 7 day immediate graft function	IA1, IA2, SAC
Acute rejection risk					
2.09	All Subjects	Non-Standard EFF_T3	Proportion of Subjects with Episodes of Biopsy-Proven Acute Rejection		IA2, SAC
2.10	All Subjects	Non-Standard EFF_T2	Summary Statistics of Episodes of Biopsy-Proven Acute Rejection		IA2, SAC
PD biomarker					
2.11	All Subjects	Non-Standard EFF_T1	Summary Statistics of Serum IP-10		IA2, SAC
2.12	All Subjects	Non-Standard EFF_T2	Summary Statistics of Serum IP-10 Change from Baseline		IA2, SAC
2.13	All Subjects	Non-Standard EFF_T1	Summary Statistics of Mig		IA2, SAC
2.14	All Subjects	Non-Standard EFF_T2	Summary Statistics of Mig Change from Baseline		IA2, SAC

Efficacy Tables					
No.	Population	IDSL / TST ID / Example Shell	Title	Programming Notes	Deliverable
2.15	All Subjects	Non-Standard EFF_T1	Summary Statistics of Free IL-18		IA2, SAC
2.16	All Subjects	Non-Standard EFF_T2	Summary Statistics of Free IL-18 Change from Baseline		IA2, SAC
2.17	All Subjects	Non-Standard EFF_T1	Summary Statistics of Bound IL-18		IA2, SAC
2.18	All Subjects	Non-Standard EFF_T2	Summary Statistics of Bound IL-18 Change from Baseline		IA2, SAC

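### The creatinine AUC formula in SAP 8.1.2 has no stop at Day 7 or Day 30, and the AUC has no rule for values lowered by dialysis

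*SAP*

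**What the plan says.** **The AUC.** SAP section 8.1.2 names three creatinine quantities: "the 7-Day Area under the Curve (AUC), 30-Day AUC and 30 Day" half-life. It gives one AUC formula, the sum from i = 1 to M of ½(Y_i + Y_{i−1})(d_i − d_{i−1}), and states that M "is the total number of measures the patient has".

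**Who enters.** For the first window, "The 7 Day AUC will be calculated based on patients who have serum creatinine value at Day 7", and "The patients who will be discharged before Day 7 will be excluded from calculation". A patient with no Day 30 value is left out as well. The programming note to Table 2.05 in section 11.9.4 repeats the first restriction: "Only consider patients who have Day 7 serum creatinine value".

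**Dialysis.** For the half-life in the same section, the starting value in a DGF patient is "the value after dialysis finished for DGF patient". In section 2.5, the intermediate and immediate graft-function categories require the creatinine fall to occur without dialysis. Nothing comparable is stated for the AUC.

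**Display.** Table 2.05, "Summary Statistics of AUC of 7 Day Serum Creatinine", and its 30-day counterpart, Table 2.06, use the Analysis Population and shell EFF_T1. That shell has no column or row for DGF or dialysis. Section 4 does not remove dialysed subjects from the Analysis Population. Both tables are due at IA1, IA2 and SAC.

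**The concern.** There are two separate issues.

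1. **Window.** The Day 7 and Day 30 sentences choose patients; they do not choose terms of the sum. In the Time and Events table (Appendix 2), clinical chemistry is taken daily until discharge and then at D30, D90, 6 and 12 months, and Appendix 7 lists creatinine under clinical chemistry. With M as all measures, a subject eligible for both AUCs gets the same number twice, and its size depends mainly on length of follow-up. Step 2 of the half-life algorithm does state its upper limit of 30, so the AUC is the one place in the section where the limit is missing.

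2. **Dialysis.** A low AUC is naturally read as good graft function. The half-life reset and the without-dialysis criteria show that the plan does not take creatinine under dialysis at face value. In the AUC those values enter unmarked. If dialysed subjects form a sizeable share (the null DGF rate in section 2.4 is 50%), the pooled mean mixes two quantities with different meanings.

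At stake is the interpretation of a summary that supports the graft-function objective and is also an IA1 output.

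**Working it through.** The SAP states no AUC value, so there is no figure to reproduce. All creatinine values below are assumptions (µmol/L). The formula is the SAP's trapezoid.

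**Step 1: the window.** Assumed subject: baseline 700, a 12% fall per day to Day 7, then 150 at D30, D90, D180 and D365, with no dialysis.

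Daily values D0–D7: 700, 616, 542.1, 477.0, 419.8, 369.4, 325.1, 286.1.

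- D0–D7: 700/2 + 616 + 542.1 + 477.0 + 419.8 + 369.4 + 325.1 + 286.1/2 = 3,242.
- D7–D30: ½ × (286.1 + 150) × 23 = 5,015, so D0–D30 = 8,257.
- D30–D365: 150 × 335 = 50,250, so all measures = 58,507.

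| Quantity | Sum stopped at the window | Formula as written | Ratio |
|---|---|---|---|
| 7-Day AUC | 3,242 | 58,507 | 18.0 |
| 30-Day AUC | 8,257 | 58,507 | 7.1 |

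With the later plateau varied from 120 to 200, the ratios run from 14.8 to 23.4 (7-day) and from 6.1 to 8.6 (30-day). If only the 12-month value is missing, the as-written figure falls by 150 × 185 = 27,750 to 30,757, although nothing has changed in the first 30 days.

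**Step 2: dialysis, with the window applied.** The comparator is the subject above. The fall at Day 7 is 1 − 286.1/700 = 59%, which is intermediate function by the 7-day rule in section 2.5.

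Dialysed graft with no function: baseline 700, a rise of 80 per day, sessions on days 1, 3 and 5, each removing 50%.

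- Sampled after each session: 700, 390, 470, 275, 355, 217.5, 297.5, 377.5. AUC = 350 + 390 + 470 + 275 + 355 + 217.5 + 297.5 + 188.75 = 2,544. This is 22% below 3,242, so the non-functioning graft looks better.
- Same subject sampled before each session: days 1, 3 and 5 become 780, 550 and 435, which adds 390 + 275 + 217.5 = 882.5. AUC = 3,426, now above 3,242.

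Sampling time alone reverses the ranking here, and section 8.1.2 does not fix it.

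**Step 3: range.** The grid crossed a rise of 50, 80, 100 or 150 per day with removal of 30, 40, 50 or 60% and sessions on days 1/3/5, 2/4/6 or 2/5, sampled after the session. This gives 4 × 4 × 3 = 48 settings. The 7-day AUC of the non-functioning graft ran from 1,730 to 6,062. It was below 3,242 in 17 settings and above it in the other 31.

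**The case against.** **The window is obvious.** The two AUCs are named by their windows, the tables carry those names, and requiring a Day 7 or Day 30 value makes sense only if that day is the end point. A reader might infer from the formula that the reported AUCs will be computed over the wrong interval. The documents do not support that, since a programmer would probably notice that two tables held the same sum and would add the cut. What stands is that the written rule gives a wrong number for both quantities and that the cut is left to the programmer. The starting index, which uses Y_0 while M counts all measures, is notation only: it is harmless if M counts post-baseline values.

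**The tables do not include everyone.** A reader might take Tables 2.05 and 2.06 as covering all treated subjects. They do not, given the Day 7 and Day 30 exclusions. Those exclusions do not depend on dialysis, however, so dialysed and non-dialysed eligible subjects are still summarised together.

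**Dialysed subjects can be traced.** Listings 23 and 24 give individual AUCs, Listing 25 gives the graft-function category and Listing 33 the dialysis events, all at IA1, IA2 and SAC. That is true and limits the harm, but it leaves the summary tables unqualified.

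**A split is not a cure.** It groups subjects by a post-treatment event, and the dialysed column still does not measure graft function. Nor does the half-life reset oblige the AUC to follow the same rule. This stands: the split labels the problem without removing it.

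**Limited role.** Section 2.2 names serum creatinine over time as the endpoint. The AUC is a derived description in a single-arm study with no test attached. This stands and sets the severity.

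**Conclusion.** Both parts hold, and both are minor. As written, one sum serves two differently named AUCs and stops at neither window. For the assumed subject the overstatement is about 18-fold for the 7-Day and 7-fold for the 30-Day AUC. These factors apply only if the formula is followed literally against its own labels.

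On dialysis, the supported statement is that a dialysed non-functioning graft can show a lower AUC than a recovering non-dialysed one, depending on dialysis and sampling times. A reader might go further and infer that pooling will generally reverse the direction of the AUC. Neither the documents nor the assumed values support that, since no reversal occurred in 31 of 48 settings and the grid is not a sample of real patients. That dialysis lowers creatinine is implied by the half-life reset and the without-dialysis criteria; it is not stated outright.

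The primary DGF analysis and the sequential decision rule are unaffected.

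**What to change.** 1. In section 8.1.2, define the sum from baseline (Y_0, d_0) over consecutive measures with d_i ≤ 7 for the 7-Day AUC and d_i ≤ 30 for the 30-Day AUC, with M as the last such measure in each case.
2. Show Tables 2.05 and 2.06 by dialysis within the window (yes/no) beside the overall column. Dialysis is a better split than DGF, because the primary endpoint leaves out dialysis for hyperkalaemia in the first 24 post-operative hours, so a subject can be dialysed without counting as DGF.
3. Flag dialysis in Listings 23 and 24.
4. Add a footnote that the AUC in dialysed subjects is not a measure of graft function.

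The cost is a few sentences, one by-group column and one flag, using dialysis data already collected. The downside is small descriptive groups (at most 30 subjects in total, fewer at IA1) formed by a post-treatment event, so the columns should be described and not compared.

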1. REPORTING & ANALYSIS PLAN SYNOPSIS

Overview	Key Elements of the RAP
Purpose	
 This RAP details all planned analyses and outputs required for the final Clinical Study Report (CSR) of study 204824.
Protocol	
 This RAP is based on the protocol (Dated: 03-FEB-2016 for study 204824 [GlaxoSmithKline Document Number: 2015N240632_01]).
Primary Objective	
 Evaluate the efficacy of single intravenous dose administrations of GSK1070806 in prevention of delayed graft function (DGF) after transplantation.
Primary Endpoint	
 Proportion of subjects requiring dialysis during the first 7 days post transplant (excluding requirement for dialysis due to hyperkalemia within first 24 post-operative hours).
Study Design	
 Pilot, multicenter, single arm Bayesian sequential design study to evaluate the efficacy, safety, tolerability and pharmacokinetics (PK) of GSK1070806 in patients undergoing renal transplantation. Sample size (maximum of 30) had been selected to yield the probability of a “go” decision of 0.139 when the GSK1070806 DGF rate is 50% and 0.69 at what has been considered to be a clinically impactful GSK1070806 DGF rate of 35%.
Planned Analyses	
 Interim analyses are detailed within Section 3.1 where applicable. All decisions regarding final analysis, as defined in this RAP document, will be made prior to Database Freeze of the study data.
Primary Analysis Population	
 The ‘Analysis Population’ will be used to evaluate DGF related endpoints The ‘All Subjects Population’ will be used to evaluate study population; safety; PD/Biomarkers and other efficacy endpoints. The ‘PK’ population will be used to evaluate pharmacokinetics. The ‘Per-Protocol’ population will be used to evaluate the DGF rate in addition to the ‘Analysis Population’.
Hypothesis	
 The study is to determine the effect of GSK1070806 on DGF. Stopping rules have been defined to test whether the DGF rate is less than or equal to the null hypothesis rate of 50%.
Primary Analyses	
 A summary of the observed DGF rate during the study will be provided. The posterior probability that the proportion of subjects experiencing DGF is less than 50% will be calculated.

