2.5. Definition of Renal Graft Function

Primary Non Function:

- Permanent lack of function of the allograft defined as an inability to discontinue dialysis from the time of transplantation. Note: The study site will decide whether patients have primary non function DGF or not and record it in data set.

3 day Functional Delayed Graft Function:

- <10% fall in SCr versus baseline per day averaged over first 3 days with OR without dialysis

7 day Functional Delayed Graft Function:

- <30% reduction in baseline SCr in first 7 days with OR without dialysis

3 day Intermediate Graft Function:

- 10- 20% fall in SCr versus baseline per day averaged over first 3 days without dialysis

7 day Intermediate Graft Function:

- 30-70% reduction in baseline Cr in first 7 days without dialysis

3 day Immediate Graft Function:

- >20% fall in SCr versus baseline per day averaged over first 3 days without dialysis

7 day Immediate Graft Function:

- >70% reduction in baseline Cr during the first 7 days without dialysis

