4. ANALYSIS POPULATIONS

Population	Definition / Criteria	Analyses Evaluated
All Subjects	
 • Comprise of subjects who receive the dose of study medication. 	
 • Safety/tolerability
Analysis	
 • For DGF related endpoints the 'Analysis Population' (AP) is defined as subjects in the 'All Subjects' population who have been declared to have DGF or have reached 7 days. For other endpoints, the AP is defined as subjects having baseline and at least one post-baseline assessment. 	
 • Efficacy • PD/Biomarker
Per Protocol	
 • Comprised of Analysis Population subjects who are compliant with protocol-specific criteria. Subjects with specified protocol deviations will be excluded per Appendix 1. 	
 • Primary efficacy endpoint
PK	
 • Subjects in the 'All Subjects' population for whom a serum pharmacokinetic sample is obtained and analyzed for GSK1070806. 	
 • PK

NOTE :

- Please refer to Appendix 10: List of Data Displays which details the population to be used for each display being generated.

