11.4. Appendix 4: Data Display Standards & Handling Conventions

11.4.1. Baseline Definition & Derivations

11.4.1.1. Baseline Definitions

For all endpoints baseline value will be the latest pre-dose assessment.

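### The creatinine half-life restarts after dialysis only for DGF patients, so in a non-DGF subject who was dialysed, dialysis clearance can shorten the reported value

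*SAP*

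**What the plan says.** Section 8.1.2 finds the half-life in three steps. Step 1 halves a starting value Y_0, which "is the baseline value for non-DGF patient and the value after dialysis finished for DGF patient"; its day is d_0. Step 2 is to "Find the time interval between d_0 and 30 where" creatinine passes from above to below that half value, and adds: "If no such interval, then report “NA” for that patient". Step 3 interpolates linearly within the interval.

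Four other places decide who is affected:

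- **DGF definition.** The synopsis and section 2.2 define the primary endpoint as dialysis in the first 7 days, "excluding requirement for dialysis due to hyperkalemia within first 24 post-operative hours".
- **Baseline.** Section 11.4.1.1: "For all endpoints baseline value will be the latest pre-dose assessment".
- **Population.** Section 11.9.4 assigns Table 2.07 ("Life of 30 Day Serum Creatinine") to the Analysis Population, with delivery at IA1, IA2 and SAC. For DGF-related endpoints, section 4 defines that population as dosed subjects "who have been declared to have DGF or have reached 7 days". For other endpoints it asks for a baseline and one later assessment.
- **Contrast.** Section 2.5 makes freedom from dialysis part of intermediate and immediate graft function, for example ">20% fall in SCr versus baseline per day averaged over first 3 days without dialysis".

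**The concern.** The DGF branch of step 1 evidently exists to keep machine clearance out of a measure of graft recovery. That protection should follow the dialysis, but the rule ties it to the DGF label, and the two differ for two kinds of subject:

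- a subject whose only dialysis was for hyperkalaemia in the first 24 hours;
- a subject free of dialysis through Day 7 and first dialysed between Day 8 and Day 30.

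Both are non-DGF under the primary endpoint and start from the pre-dose baseline. The search window includes the dialysis interval, and no other section resets or sets aside the creatinine values that follow it. Table 2.07 may then report a subject who needed dialysis as a fast recoverer. The table is one of the graft-function displays in the IA1 and IA2 packages, where few subjects are summarised and one value can move a mean.

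**Working it through.** The SAP states no figure for the half-life, so there is none to reproduce. The check follows the rule for one subject and then runs the three steps on assumed curves.

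**Following the rule.** Take a subject dialysed once, at 12 hours, for hyperkalaemia.

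1. The synopsis exclusion applies, so the subject is non-DGF.
2. Step 1 therefore sets Y_0 to baseline, which section 11.4.1.1 places before dosing and hence before the dialysis.
3. Step 2 searches from that day to Day 30, so the dialysis interval is inside the window.
4. The subject meets either wording of the Analysis Population in section 4 by reaching Day 7 with a baseline and later values, and so enters Table 2.07.

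**Assumed inputs (none is in the SAP).** Baseline is 800 µmol/L. Samples are at day 0, 6 hours, daily from Day 1 to Day 14, and Day 30. One session between 6 hours and the Day 1 sample cuts creatinine by a fraction f of 0.2 to 0.7. A working graft clears the excess over 120 µmol/L with a half-life of 3, 5 or 8 days; a non-working graft clears nothing.

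**Formula.** Y_1/2 = Y_0/2 = 400, and d_1/2 = (Y_1/2 − Y_i)/(Y_{i+1} − Y_i) × (d_{i+1} − d_i) + d_i.

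**One case in full: 8-day graft half-life, f = 0.5.**

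- At 6 hours: 120 + 680 × 2^(−0.25/8) = 785.4.
- At Day 1: (120 + 680 × 2^(−1/8)) × 0.5 = 743.6 × 0.5 = 371.8.
- d_1/2 = (400 − 785.4)/(371.8 − 785.4) × 0.75 + 0.25 = 0.95.

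**Result under the rule as written, in study days:**

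| Graft half-life | No dialysis | f = 0.2 | 0.3 | 0.4 | 0.5 | 0.6 | 0.7 |
|---|---|---|---|---|---|---|---|
| 3 days | 3.86 | 2.65 | 1.88 | 0.99 | 0.88 | 0.79 | 0.73 |
| 5 days | 6.42 | 4.43 | 3.18 | 1.68 | 0.92 | 0.82 | 0.75 |
| 8 days | 10.25 | 7.10 | 5.14 | 2.77 | 0.95 | 0.84 | 0.76 |
| No clearance | NA | NA | NA | NA | NA | 0.88 | 0.79 |

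With a working graft, every assumed session shortens the result. The crossing lies in the dialysis interval itself only when the Day 1 value is below 400. With the 8-day graft that means f > 1 − 400/743.6 = 0.46. With no graft clearance it means f > 0.5, and at or below that the rule correctly returns NA. If creatinine falls to 320 and climbs back to 800, the rule still gives (400 − 800)/(320 − 800) × 0.75 + 0.25 = 0.88.

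**Effect on a mean.** Suppose 10 subjects are summarised (assumed) and one is affected, with an 8-day graft. The mean falls by (10.25 − 7.10)/10 = 0.32 day at f = 0.2 and by (10.25 − 0.95)/10 = 0.93 day at f = 0.5. With 30 subjects these shifts are one third as large.

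**Restarting at the Day 1 post-dialysis value.** At f = 0.5 the 8-day graft moves from day 0.95 to day 18.11, and the 5-day graft from 0.92 to 11.13. The non-working graft at f = 0.6 moves from 0.88 to NA. The restart does not recover the undisturbed 10.25 or 6.42: it asks for a halving from a lower level. At f = 0.7 all three working grafts become NA; for the 8-day graft, half of 743.6 × 0.3 is 111.5, below the assumed floor of 120. The existing DGF branch has the same property.

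**Two loose ends in the same steps.** The SAP does not say which crossing to use when creatinine rebounds; one test curve gave both 0.91 and 5.50. Also, d_1/2 is a study day, not time since d_0, which matters once d_0 is not zero.

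**The case against.** Several counter-arguments are fair, and most limit the point without removing it.

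- **Dialysis does not always produce the half-life.** A reader might infer that any such subject receives a half-life made by the machine. The documents do not support that. It holds only when creatinine falls below half of baseline across the dialysis interval, and the SAP gives no figure for the fall in a session. With smaller falls the value is shortened, or stays NA if the graft clears nothing.
- **The slowest subjects are not silently lost.** A reader might also infer that NA hides poor recoverers. Shell EFF_T1 prints N and n, so the number of NA results is visible, though not the reasons. Primary non function is in Table 2.08, dialysis independence in Table 2.24 and dialysis events to Day 30 in Listing 33. Reporting NA is open handling, not an error.
- **Some cross-checks exist.** A very short value would show as the minimum in Table 2.07, and Figure 2.01 shows individual creatinine curves from IA1 on. However, Table 3 promises a half-life listing and section 11.9.11 contains none, so no listing shows the individual half-lives.
- **The group may be empty.** The SAP gives no expected number, and any rate would be a guess.
- **Little depends on it.** The sequential rule uses DGF counts, the primary analysis is the DGF rate, and section 2.2 does not name half-life among the endpoints. That Table 2.07 would sway the IA1 dose review is an inference from its place in the delivery list.

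None of this supplies the missing rule. For a dialysed non-DGF subject, section 8.1.2 as written still counts dialysis clearance as graft recovery.

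**Conclusion.** The point stands in a limited form. Step 1 attaches the post-dialysis restart to the wrong condition. A non-DGF subject dialysed for early hyperkalaemia keeps the pre-dose baseline, so dialysis can shorten the reported half-life. The same applies to a subject first dialysed between Day 8 and Day 30 who has not already halved.

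That the rule leaves this gap follows from the text alone. Its size rests on assumed curves: with an 8-day graft half-life, day 10.25 becomes day 7.10 to 0.76 for session falls of 20% to 70%. The number of subjects affected is unknown and may be zero.

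The consequence is confined to one descriptive summary, Table 2.07, at IA1, IA2 and SAC. A stronger conclusion, that the trial's decision or its primary result is distorted, is not supported: neither the DGF rate nor the Go/No Go rule uses the half-life. The change is still worth making, because a rule followed exactly should not credit dialysis to the graft and the repair is small.

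**What to change.** In section 8.1.2 step 1, replace the non-DGF/DGF split with: subjects with no dialysis between transplant and Day 30, who start from baseline; and subjects with any dialysis in that period, whatever the indication, who start from the post-dialysis value the plan already uses, with d_0 as its day. The Day 30 limit keeps d_0 inside the search window, and the starting value for DGF patients is otherwise left as it is.

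Optionally, footnote Table 2.07 with the number reported as NA, split into those still on dialysis at Day 30 and those whose creatinine had not halved by Day 30.

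The cost is a wording change and a small programming change; the Time and Events table already collects dialysis events. The summary may look slightly less favourable, since restarted values run longer and some become NA. A subject who had halved before a first dialysis after Day 7 would also lose that earlier value, so the sponsor should confirm that this is intended.

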11.2. Appendix 2: Time and Events

Study Day ¹	Screening	Pre-operative (baseline)	Intra-operative (D0) ¹	4-8h ²	D1	D2	Daily until discharge	Discharge	D30	D90	6 & 12 months ¹³	Unscheduled Visit
Informed Consent/Demographics	X											
Medical/drug/alcohol/tobacco history	X											
GSK1070806 IV Infusion			←-----→ ¹⁵									
Kidney preservation fluid IL-18			X ¹⁶									
Kidney biopsy (post-reperfusion) ³			X (~45 min)									
Clinical biopsy reports (if applicable)			←-----→									
Concomitant medication	X	X	X ¹⁷	X	X	X	X	X	X	X	X	X
Evidence of infection	X			X	X	X	X	X	X	X	X	X
SAE / AE monitoring			←-----→									
DGF status (up to day 7)				←-----→								
Urine output		X (native output)	X	X	X	X	X					
Dialysis events since last assessment		X		X	X	X	X	X	X	X	X	X
Graft survival			←-----→									
Viral serology (recipient & donor – HIV, Hep B/C, EBV) ⁴	X ⁵	X									X	X
Viral serology (recipient & donor -herpes, varicella) ⁴		X										
CMV monitoring	X ⁵	X									X	X
BK virus monitoring ⁶		X							X	X	X	X
Vital signs ⁷	X			X	X	X	X	X	X	X	X	X
Complete physical	X										X	X
12-lead ECG	X							X			X	X
Hematology / Clinical Chemistry / Urinalysis	X			X	X	X	X	X	X	X	X	X
Pregnancy test ⁸	X								X	X	X	X
Serum cytokines / PD biomarkers		X ¹¹	X (~45 min at biopsy)	X	X	X		X	X	X	X	X

Study Day ¹	Screening	Pre-operative (baseline)	Intra-operative (D0) ¹	4-8h ²	D1	D2	Daily until discharge	Discharge	D30	D90	6 & 12 months ¹³	Unscheduled Visit
Free, GSK1070806 bound & total IL18 ⁹		X ¹¹	X (~45 min at biopsy)	X	X	X		X	X	X	X	X
Pharmacokinetics ^{9,10}		X ¹¹	X (~45 min at biopsy)	X	X			X (@168 hrs or at earlier discharge)	X	X	X	X
Immunogenicity ¹²		X ¹¹							X	X	X	X
Urinary biomarkers		X ¹¹		X	X	X	X	X	X	X	X	X
Peripheral blood leucocyte flow phenotyping ¹⁴		X						X		X	X	
PBMCs frozen for in vitro stimulation assays ¹⁴		X						X		X	X	
PBMCs placed in trizol for transcriptomic analysis ¹⁴		X						X		X	X	

1. Day 0 defined as the calendar day of transplant.
2. Time post reperfusion.
3. Biopsies during transplantation may be 'core or wedge' at the discretion of the operating surgeon. If, in the judgement of the operating surgeon, biopsy poses unwarranted risk to the patient, it may be omitted.

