11.5. Appendix 5: Derived and Transformed Data

11.5.1. General

Multiple Measurements at One Time Point

- Mean of the measurements will be calculated and used in any derivation of summary statistics but if listed, all data will be presented.
- If there are two values within a time window the value closest to the target day for that window will be used. If values are the same distance from the target then the mean will be taken.
- Subjects having both High and Low values for Normal Ranges at any post-baseline visits for safety parameters will be counted in both the High and Low categories of “Any visit post-baseline” row of related summary tables. This will also be applicable to relevant Potential Clinical Importance summary tables.

Study Day

- Calculated as the number of days from dosing date :
 - [1] Assessment Date = Missing → Study Day = Missing
 - [2] Assessment Date < Transplant Date → Study Day = Assessment Date – Transplant Date
 - [3] Assessment Date \geq Transplant Date → Study Day = Assessment Date – Transplant Date

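### The creatinine half-life in SAP Section 8.1.2 is a study day, not an elapsed time, so for DGF subjects it includes the days before dialysis ended

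*SAP*

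**What the plan says.** SAP Section 8.1.2 sets out three steps.

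- Step 1 halves a reference value Y_0, which is "the baseline value for non-DGF patient and the value after dialysis finished for DGF patient", and names its day d_0.
- Step 2 searches for the crossing: "Find the time interval between d_0 and 30 where" creatinine passes from above to below half of Y_0. If there is no such interval, the subject gets NA.
- Step 3 interpolates linearly within that interval, adds d_i, and calls the result the approximate half-life. d_0 does not appear in the formula.

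Days count from transplant. A note to the Time and Events table (Section 11.2) reads "Day 0 defined as the calendar day of transplant". Section 11.5.1 subtracts the transplant date from the assessment date, including where "Assessment Date < Transplant Date", so earlier days are negative. On baseline, Section 11.4.1.1 says: "For all endpoints baseline value will be the latest pre-dose assessment".

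The result goes into Table 2.07 (Section 11.9.4, title ending "Life of 30 Day Serum Creatinine"). This is a single Analysis Population table with shell EFF_T1, due at IA1, IA2 and the final analysis. It has no programming note, and the shell shows one treatment group with no DGF row. Table 3 in Section 8.1.1 marks an individual half-life listing, but none of Listings 1 to 41 is one.

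**The concern.** A half-life should measure how long a value takes to halve from its starting point. Here the starting point of a DGF subject lies after dialysis, yet the clock runs from transplant. Two subjects whose creatinine falls equally fast get different numbers if one came off dialysis later. Table 2.07 then averages these numbers with those of non-DGF subjects, whose reference is the pre-dose value. A reader of the pooled mean could not tell slow recovery from a late end of dialysis. This matters most at IA1, planned after about 8 to 10 patients, where a single subject carries much of the mean.

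**Working it through.** **Plan's own figure.** The SAP states no half-life value, so there is none to reproduce. The check is algebra on steps 1 to 3, followed by illustrations.

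**Algebra.** Let f = (Y_1/2 − Y_i)/(Y_(i+1) − Y_i).

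- Reported: d_1/2 = d_i + f × (d_(i+1) − d_i), a study day.
- Elapsed since Y_0: d_1/2 − d_0.
- Reported minus elapsed: d_0.

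This identity needs no assumption. Step 2 ends the search at Day 30, so only subjects with d_0 below 30 can have a value.

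**Illustration per subject (assumed curve).** Creatinine = 120 + 480 × exp(−(t − d_0)/5), sampled daily, so Y_0 = 600 and half is 300. With d_0 = 0 the Day 4 and Day 5 values are 335.7 and 296.6. Then f = (300 − 335.7)/(296.6 − 335.7) = 0.91 and d_1/2 = 4.91.

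| d_0 | Reported | Reported − d_0 |
|---|---|---|
| 0 | 4.91 | 4.91 |
| 2 | 6.91 | 4.91 |
| 7 | 11.91 | 4.91 |
| 14 | 18.91 | 4.91 |

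A second assumed curve (exponential fall with a halving time of 3.3 days) gives 3.32 at d_0 = 0, 10.32 at d_0 = 7 and 29.32 at d_0 = 26. It gives NA at d_0 = 27, because the crossing falls after Day 30.

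**Pooled mean.** Count non-DGF subjects from Day 0, and let q be the DGF share among subjects who have a value. The mean shifts by q × mean d_0. Both quantities are assumed here.

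| q | d_0 = 2 | d_0 = 7 | d_0 = 14 |
|---|---|---|---|
| 0.1 | 0.2 | 0.7 | 1.4 |
| 0.2 | 0.4 | 1.4 | 2.8 |
| 0.3 | 0.6 | 2.1 | 4.2 |
| 0.4 | 0.8 | 2.8 | 5.6 |

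The median behaves differently. Take seven non-DGF and three DGF subjects (d_0 = 7), all with an elapsed time of 4.91. The mean is (7 × 4.91 + 3 × 11.91)/10 = 7.01, while the median stays at 4.91. At IA1 size, one DGF subject with d_0 = 14 among eight values moves the mean by 14/8 = 1.75 days.

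**Why q is not the DGF rate.** The 50% and 35% in Section 1 are rates among all subjects. A DGF subject with no post-dialysis value, or with no crossing by Day 30, drops out of Table 2.07. On a curve with plateau 120 and d_0 = 7, a post-dialysis Y_0 of 220 or 240 never crosses its half (110 or 120) and gives NA. A Y_0 of 260 crosses 130 at Day 20.2.

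**Non-DGF subjects.** In Section 11.2 the row "Hematology / Clinical Chemistry / Urinalysis" is marked at screening and next at 4-8 h, so the baseline sample may precede transplant. With an assumed baseline of 600 on Day −1 and the decline starting on Day 0, step 3 reports 4.91, against 5.91 days since the sample. The extra day is one with no graft in place.

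**The case against.** The strongest defence is notational. In Section 8.1.2 the letter d always stands for a day, the window ends at Day 30 after transplant, and the output is written d_1/2. Read that way, step 3 correctly gives the study day on which creatinine reached half of Y_0. This is coherent, and it is why relabelling is an acceptable remedy. But the SAP calls the result a half-life and nowhere states the other meaning. Even on that reading, the pooled row mixes days tied to a pre-dose reference with days tied to a post-dialysis one.

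It may also be said that EFF_T1 is only an example shell and must be adapted, since its visit and planned-time columns do not suit one value per subject. That is fair, but neither the Table 2.07 entry nor any other section provides a split.

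Some stronger readings are tempting, and the SAP does not support them.

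- A reader might infer that every DGF value is too long. The excess is zero if d_0 is Day 0, and some DGF subjects have no value at all.
- A reader might infer that non-DGF values are wrong too, because d_0 is not subtracted there either. Subtracting it could add pre-transplant days; a clock from Day 0 is sensible for these subjects and only needs stating.
- A reader might treat the strict inequalities, repeat crossings or the Day 30 rule as further errors. The first two are programming detail. The sentence "If the value is missing, the patient will be excluded from calculation" belongs to the AUC text, and half-life has its own NA rule in step 2.

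**Conclusion.** The point holds as a minor error in a supportive descriptive table. What follows from the document alone is that a DGF value with d_0 above zero exceeds the elapsed halving time by exactly d_0, and that Table 2.07 pools such values with non-DGF values.

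The size of the pooled effect cannot be derived, because the SAP gives neither the end of dialysis nor the share of DGF subjects with a value. The range of 0.2 to 5.6 days rests on assumed inputs and a Day 0 clock for non-DGF subjects. Since the SAP fixes no such clock, the net direction is not established either, and the median may not move.

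Half-life is not among the endpoints in Section 2.2. Creatinine over time is, and Tables 2.03 and 2.04 report it directly. Listings 22, 25 and 33 let a reader rebuild most of the inputs. A reader might infer a threat to the main result, but the primary DGF rate and the sequential rule do not use this variable.

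**What to change.** In Section 8.1.2, for DGF subjects report d_1/2 − d_0, and say which post-dialysis sample supplies Y_0 so that d_0 is its day. For non-DGF subjects state a Day 0 origin, so that pre-transplant days are not counted. Alternatively, keep the formula and relabel the variable as the *study day on which creatinine reached half of Y_0*.

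Under either option, show DGF and non-DGF subjects separately in Table 2.07, because their reference values differ even after d_0 is subtracted. Add the individual half-life listing that Table 3 marks, and show d_0 in it.

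The cost is a few lines of SAP wording, at most a one-term program change, a split table and one listing. The drawback is fewer subjects per row and so less precise group means, most of all at IA1.
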